3.3 STUDY DRUG ADMINISTRATION AND EXTENT OF EXPOSURE

3.3.1 Dose Limiting Toxicity and Progression of Groups

New participants will not be enrolled into the next higher dosage group until at least 8 participants in the previous cohort have completed the SD 8 follow-up visit without the occurrence of DLTs and the DSMB has made a recommendation to the sponsor regarding dose escalation. The sponsor must approve the dose escalation and notify the investigator(s) before any new participants can be enrolled. The occurrence of any extreme DLT(s) or serious adverse events (SAEs), except unrelated, would result in the immediate discontinuation of dosing and study enrollment, pending a review of study data by the PI, the DSMB, and the sponsor. Nonextreme DLTs can result in halting of dosage pending review. Enrollment will also be halted if two nonextreme DLTs occur in the first four participants in a cohort or 3 participants in total.

Table 3: Progression of Dosing Related to Dose-Limiting Toxicity Events

Dose-Limiting Toxicity	Number of Participants	Action	Follow-up
Extreme DLT	1	Dosing and enrollment halted	PI and DSMB to make recommendation to sponsor whether trial should continue
Nonextreme DLT	1 of first 4 in a cohort (or 2 in the first 8)	Dosing halted	PI and DSMB to make recommendation to sponsor whether to increase cohort size from 8 to 12
	2 of the first 4 in a cohort (or 3 total)	Dosing and enrollment halted	PI and DSMB to make recommendation to sponsor whether trial should continue
SAE not already designated as a DLT (except unrelated)	1	Dosing and enrollment halted	DSMB to make recommendation to sponsor whether trial should continue

3.4 STUDY POPULATION

[figure not shown]
The study will include up to 60 male and female volunteers, 18 to 55 years of age, who will be enrolled in 5 dosing groups (cohorts) of 8 to 12 participants each. The actual number enrolled in the study will be determined by the safety responses noted during the study. Each of the 5 cohorts will include at least 3 male and 3 female participants enrolled among the first 8 participants in the cohort to ensure that at least 1 male and 1 female subject in each dosing group receive active drug. Each cohort will include 6 to 9 individuals receiving active and 2-3 receiving placebo doses (total of 30-45 active and 10-15 placebo).

3.5 SAMPLE SIZE CALCULATION/JUSTIFICATION

The planned sample of 40-60 healthy participants was chosen to provide a cohort size of 8-12 per dose (6-9 active, 2-3 placebo). This cohort size is customary in Phase 1 clinical trials with safety and tolerability as primary endpoints as it allows detection of common dose-limiting

toxicities or SAEs. In a cohort of N individuals dosed with the active drugs, the probability that one non-extreme DLT or SAEs with a true probability of occurrence, p , will be observed is $1 - (1 - p)^N$. There is 80% chance that at least one event with true probability of occurrence of 23.5% will occur within a cohort of 6 active participants. In a cohort of 8 participants, there is 80% probability of an event occurring if its true probability of occurrence is 18.2%. The addition of placebo controls is intended to help distinguish drug-related and unrelated events and for comparison of injection site reactions, cognitive, and neuropsychiatric responses.

Figure 1: Power to Detect an Adverse Event with Probability of Occurrence, P , in an Active Drug Cohort of Size N

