12.2. Planned Enrollment and Reason for Sample Size

The sample size calculation of 40-60 healthy subjects has been chosen to provide adequate numbers of subjects for characterization of the safety and tolerability of Scopolamine HBT administered in 1 to 5 dose-escalating cohorts in normal, healthy volunteers as well as a placebo group. No formal statistical sample size computation was performed; however, the 6 to 9 active subject and 2 to 3 control subject design is commonly employed in Phase 1 clinical trials because it provides adequate power to detect non-rare events (true probability, $P > 0.20-0.25$) events within each cohort. Enrollment may be stopped at any dosing level if stopping criteria are met; therefore, the total sample size may be substantially smaller than 40-60.

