3.6 RANDOMIZATION SCHEME

Participants will be randomized to receive either active Scop HBT or placebo injections using a blocked randomization design. In each cohort, 6 to 9 participants will receive active drug and 2 to 3 participants will receive placebo. Each cohort will have at least at least 3 male and 3 female participants enrolled among the first 8 participants in the cohort to ensure that at least 1 male subject and 1 female subject in each dosing group receive active drug. The study PI will create cohorts of 8 to 12 participants. If a participant withdraws or is excluded, the participant will be replaced by a participant of the same or opposite sex so long as the sex of all participants in the block conforms to the requirements.

Randomization will assign cohort members to active Scop HBT or Placebo at a ratio of 3 active to 1 placebo. Randomization will be conducted using blocking with three different block sizes per cohort. A block of 2 (1 active and 1 placebo) will be used for the first two participants in each cohort (Table 4A). A block of 6 (5 active and 1 placebo) will be used to assign the next 6 participants in each cohort (Table 4B). A block of 4 (3 active and 1 placebo) will be used to randomized participants in a possible expansion cohort. The blocks will be randomly permuted using a randomization program for each dosage level to yield a randomization plan.

Table 4: Blocks with Sample Randomization Assignment

A. Block of Two for the First Two Participants in a Cohort

Participant Order	Randomization Assignment (Only visible to unblinded individuals)
1	Placebo
2	Active Scop HBT

B. Block of Six for Third to Eighth Participants in a Cohort

Participant Order	Randomization Assignment (Only visible to unblinded individuals)
3	Active Scop HBT
4	Active Scop HBT
5	Active Scop HBT
6	Active Scop HBT
7	Placebo
8	Active Scop HBT

C. Block of Four for Cohort Expansion Participants

Participant Order	Randomization Assignment (Only visible to unblinded individuals)
9	Active Scop HBT
10	Placebo
11	Active Scop HBT
12	Active Scop HBT

For cohorts of 8 participants, only the first two blocks will be used. The third block will be used only if the cohort is expanded from 8 to 12. A sample randomization assignment for a dosing cohort is included in [Table 5](#).

Table 5: Sample Randomization Scheme for a Dosing Cohort

Cohort	Block	Participant	Sex	Randomization Assignment (Only visible to unblinded individuals)
Primary (N=8)	1	1	F	Placebo

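### SAP 3.5 gives a cohort of 8 participants an 80% chance of showing an event with an 18.2% rate; with the 6 on active drug in such a cohort, the chance is 70.0%

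*SAP*

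**What the plan says.** SAP 3.5 justifies the cohort size by the chance of seeing at least one toxicity of a given true probability p. It defines the exposed group first, "In a cohort of N individuals dosed with the active drugs", and gives the probability of observing an event as 1 − (1 − p)^N. The title of Figure 1 uses the same convention, since it refers to an active drug cohort of size N.

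Two worked figures follow, both set at an 80% chance. The first is for a "true probability of occurrence of 23.5% will occur within a cohort of 6 active participants". The second reads: "In a cohort of 8 participants, there is 80% probability of an event occurring if its true probability of occurrence is 18.2" (percent).

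The make-up of a cohort is stated in several places. SAP 3.4: "Each cohort will include 6 to 9 individuals receiving active and 2-3 receiving placebo doses". SAP 3.6: "Randomization will assign cohort members to active Scop HBT or Placebo at a ratio of 3 active to 1 placebo". SAP 3.6 then sets the blocks. The first two participants are 1 active and 1 placebo, the next six are 5 active and 1 placebo, and a possible expansion block of four is 3 active and 1 placebo. A cohort of 8 uses only the first two blocks.

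Protocol 12.2 reports that no formal sample size computation was made. It says of the 6-to-9 active design that "it provides adequate power to detect non-rare events", meaning events with a true probability above 0.20–0.25.

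**The concern.** The two worked figures in SAP 3.5 use different bases. The first counts participants on active drug, as the formula requires. The second appears to put the total cohort size into the same formula, so that two placebo participants are treated as exposed.

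The first figure is for 6 active participants and the second is for a cohort of 8, but under SAP 3.6 these are the same cohort. Consecutive sentences therefore give it two different thresholds, 23.5% and 18.2%, at the same 80% chance. The second is the more favourable. If it were carried into the study report, the standard cohort would appear able to show rarer toxicities than it can. Safety is a primary objective, so a stated detection probability should match the number of people exposed.

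**Working it through.** **Inputs**

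- Formula: P(at least one event) = 1 − (1 − p)^N, with N the number on active drug (SAP 3.5).
- Stated pairs: 80% at p = 0.235 for 6 active; 80% at p = 0.182 for a cohort of 8 (SAP 3.5).
- Active participants in a cohort of 8: 1 + 5 = 6, with 1 + 1 = 2 on placebo (SAP 3.6).
- Active participants in an expanded cohort of 12: 6 + 3 = 9, with 3 on placebo (SAP 3.6; the footnote to Table 8 in SAP 6.4 also gives 9 as the maximum).

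**Step 1. Reproduce the SAP's figures**

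- N = 6, p = 0.235: 1 − 0.765^6 = 0.7996. This matches the stated 80%.
- N = 8, p = 0.182: 1 − 0.818^8 = 0.7995. This matches the stated 80%, but only with 8 participants exposed.

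**Step 2. Put in the actual number exposed at p = 18.2%**

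- Standard cohort, N = 6: 1 − 0.818^6 = 0.7004, or 70.0%. The chance of seeing no such event is 30.0%, where the SAP's sentence implies 20%.
- Expanded cohort, N = 9: 1 − 0.818^9 = 0.8360, or 83.6%.

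**Step 3. Solve for the rate that gives 80%:** p = 1 − 0.2^(1/N)

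| On active drug | Planned cohort | Rate with 80% chance of at least one event |
|---|---|---|
| 6 | standard, 8 participants | 23.5% |
| 8 | no full cohort | 18.2% |
| 9 | expanded, 12 participants | 16.4% |

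**Step 4. Could the placebo participants account for the 80%?** Let b be an event rate on placebo. The chance of any event among all 8 participants is 1 − 0.818^6 × (1 − b)^2. The documents give no value for b, so these are assumptions:

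- b = 0%: 70.0%
- b = 5%: 73.0%
- b = 10%: 75.7%
- b = 18.2%: 80.0%

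The stated figure returns only if placebo carries the same event rate as the drug. That would also depart from the SAP's own definition of N.

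**Step 5. Compare with protocol 12.2.** With 6 active, the chance is 1 − 0.80^6 = 73.8% at p = 0.20 and 1 − 0.75^6 = 82.2% at p = 0.25. The protocol's range brackets the 23.5% figure.

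**The case against.** The strongest defence is that the sentence means 8 active participants. The paragraph defines N that way, the title of Figure 1 repeats it, and for N = 8 the arithmetic is right. Eight also lies inside the stated range of 6 to 9 active, and could arise if an expansion were halted part-way.

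This defence does not rescue the sentence. SAP 3.6 uses a cohort of 8 participants for the one with 6 active and 2 placebo, and SAP 3.5 says active participants in the preceding sentence when it means that. A part-filled expansion with 8 active would hold 10 or 11 participants in total, not 8. Even on the kind reading, the figure describes no full planned cohort.

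The rest of the defence concerns consequence, and it stands. A reader might infer four larger faults that the documents do not support:

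- *That the sample size justification rests on a wrong number.* The correct 23.5% for 6 active is in the preceding sentence, and Table 8 in SAP 6.4 gives upper confidence bounds for 6 and 9 active (for example 0.32 for no events in 6, and 0.37 for one event in 9). SAP 3.5 calls the cohort size customary.
- *That the plan gives no detection figure for the expanded cohort.* The text of SAP 3.5 gives none, but Figure 1 is not reproduced in the text available for this review and may include N = 9.
- *That protocol 12.2 is also wrong.* It claims adequate power without naming 80%, and its range is compatible with 6 active (Step 5).
- *That dosing decisions are affected.* The halting rules in SAP 3.3.1 count events and do not refer to 18.2%.

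**Conclusion.** The sentence is wrong as written, and the point is minor. For the cohort that it names, the probability is 70.0% rather than 80%, a shortfall of 10 percentage points. Put the other way, the rate that the cohort shows with 80% probability is 23.5% rather than 18.2%. The calculation is correct for 8 exposed participants. The fault lies in using total cohort size where the formula calls for the number on active drug.

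This rests on the SAP's own formula, which assumes independent events with a common probability, and on a complete cohort randomized as in SAP 3.6. It does not show that the trial is too small or that any rule or analysis needs to change.

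**What to change.** Make two edits in SAP 3.5:

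1. State that the 23.5% figure applies to the standard cohort of 8 participants (6 active).
2. Replace the 18.2% sentence with: *In an expanded cohort of 12 participants (9 active), the corresponding rate is 16.4%.*

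The cost is a label and one replaced sentence. The unsupported figure for the standard cohort goes, and both planned cohort sizes then have a stated detection rate. Protocol 12.2, the sample size and the stopping rules need no change.

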3.6 RANDOMIZATION SCHEME

Participants will be randomized to receive either active Scop HBT or placebo injections using a blocked randomization design. In each cohort, 6 to 9 participants will receive active drug and 2 to 3 participants will receive placebo. Each cohort will have at least at least 3 male and 3 female participants enrolled among the first 8 participants in the cohort to ensure that at least 1 male subject and 1 female subject in each dosing group receive active drug. The study PI will create cohorts of 8 to 12 participants. If a participant withdraws or is excluded, the participant will be replaced by a participant of the same or opposite sex so long as the sex of all participants in the block conforms to the requirements.

Randomization will assign cohort members to active Scop HBT or Placebo at a ratio of 3 active to 1 placebo. Randomization will be conducted using blocking with three different block sizes per cohort. A block of 2 (1 active and 1 placebo) will be used for the first two participants in each cohort (Table 4A). A block of 6 (5 active and 1 placebo) will be used to assign the next 6 participants in each cohort (Table 4B). A block of 4 (3 active and 1 placebo) will be used to randomized participants in a possible expansion cohort. The blocks will be randomly permuted using a randomization program for each dosage level to yield a randomization plan.

Table 4: Blocks with Sample Randomization Assignment

A. Block of Two for the First Two Participants in a Cohort

Participant Order	Randomization Assignment (Only visible to unblinded individuals)
1	Placebo
2	Active Scop HBT

B. Block of Six for Third to Eighth Participants in a Cohort

Participant Order	Randomization Assignment (Only visible to unblinded individuals)
3	Active Scop HBT
4	Active Scop HBT
5	Active Scop HBT
6	Active Scop HBT
7	Placebo
8	Active Scop HBT

C. Block of Four for Cohort Expansion Participants

Participant Order	Randomization Assignment (Only visible to unblinded individuals)
9	Active Scop HBT
10	Placebo
11	Active Scop HBT
12	Active Scop HBT

For cohorts of 8 participants, only the first two blocks will be used. The third block will be used only if the cohort is expanded from 8 to 12. A sample randomization assignment for a dosing cohort is included in [Table 5](#).

Table 5: Sample Randomization Scheme for a Dosing Cohort

Cohort	Block	Participant	Sex	Randomization Assignment (Only visible to unblinded individuals)
Primary (N=8)	1	1	F	Placebo
		2	M	Active Scop HBT
	2	3	M	Active Scop HBT
		4	F	Active Scop HBT
		5	F	Active Scop HBT
		6	M	Active Scop HBT
		7	M	Placebo
		8	M	Active Scop HBT

Expansion (N=4)	3	9	F	Active Scop HBT
		10	F	Placebo
		11	F	Active Scop HBT
		12	M	Active Scop HBT

4. ANALYSIS SETS

4.1 INTENT-TO-TREAT POPULATION

The Intent-To-Treat Population is defined as all participants who are enrolled and randomized into the trial.

4.2 SAFETY POPULATION

The Safety Population consists of all participants who received any amount of study medication, regardless of disposition. All safety analyses will be performed on this population.

4.3 PHARMACOKINETICS POPULATION

The PK Population will include any subject who receives a dose of active Scop HBT and has at least one blood draw to determine the concentration of scopolamine in plasma or one urine sample to determine concentration in urine. All PK analyses will be performed on this population. Please note, the calculation of PK parameters will not be described or performed within this SAP. A separate PK manual and the report will detail the procedures, results, and limitations for the PK parameters.

4.4 OTHER ANALYSIS POPULATIONS (INCLUDING SUBGROUPS)

No subgroup analyses are proposed. PK analyses will include adjustment for sex of the participant. Although no additional analyses of sub-populations are planned at this time, additional populations and analyses may be conducted at the discretion of the Sponsor to supplement the results or for research purposes. Analysis of subgroups conducted after the final SAP is approved will be labeled as “post hoc” in the final statistical report/and or CSR.

4.5 TREATMENT MISALLOCATIONS

Should any treatment misallocations occur, all participants will be analyzed in the Safety and PK populations “As Treated” instead of “As Randomized”. Due to the nature of this study whereby the biological effect of the study medication is being examined without respect to efficacy assessment, analyzing the participants “As Treated” is sufficient. A listing will be provided to display any participants with treatment misallocations, should they occur.

5. ENDPOINTS AND COVARIATES

5.1 SAFETY ENDPOINTS

The first objective of this study is to characterize the safety of Scop HBT at varying dosages. The study specifically defines three types of safety endpoints in the protocol: extreme dose-limiting toxicities (DLTs), nonextreme DLTs, and serious adverse events (SAEs) related to the drug. Any events or issues not defined as extreme/nonextreme DLTs or SAEs will be considered as Adverse Events (AEs). In addition to AEs, data will be collected and analyzed on injection site

assessments and changes in cognitive function, neuropsychiatric status, vital signs, clinical laboratory results, heart rhythm, and physical health status.

5.1.1 Extreme Dose-Limiting Toxicities

Extreme DLTs include specific respiratory, neuropsychiatric, cardiac, renal, and severe injection site reaction events as outlined below and in the protocol section 7.6.1.1. These events are defined in the protocol and will be determined by the study PI, Pharmacovigilance physician, and DSMB. These extreme DLTs include:

- Respiratory
 - Prolonged apnea or respiratory distress where intubation is required
- Neuropsychiatric
 - Presence of convulsions or seizure-like activity
 - Neuropsychiatric symptoms (e.g., delirium, paranoia, and/or hallucinations) requiring treatment with physostigmine or other medication(s) and, in the opinion of the investigator, did not adequately respond to treatment
- Cardiovascular
 - Cardiac arrest
 - Clinically significant hypotension that requires IV fluids or vasopressors
 - Cardiac arrhythmias
 - 1^{o} AV block (if the PR interval becomes \geq 280 milliseconds)
 - If the QRS duration increases by more than 25% from the pre-dose measurement and is $>$ 140 msec
 - QTc (Fridericia) is $>$ 500 msec and increase of QTc of 60 msec from baseline
 - AV block (2nd degree, 3rd degree)
 - Bundle branch block
 - Bigeminy or trigeminy associated with hypotension
 - Atrial fibrillation or atrial flutter

5.1.2 Nonextreme Dose-Limiting Toxicities

Nonextreme DLTs are AEs that do not meet the criteria for extreme DLTs but are serious conditions that require immediate medical attention and monitoring. Nonextreme DLTs include:

- Respiratory
 - Spontaneous respiratory rate $<$ 8 or $>$ 25 breaths per minute, with oxygen saturation less than 90%, which cannot be explained by agitation or other behavioral symptoms and that does not respond immediately to oxygen supplementation via nasal cannula or face mask but for which there is recovery without sequelae prior to the need for intubation

- Dyspnea at rest
 - Symptomatic bronchospasm
- Neuropsychiatric
 - Neuropsychiatric symptoms (e.g., delirium, paranoia, and/or hallucinations) requiring treatment with physostigmine or other medication(s) and, in the opinion of the investigator, responded adequately to treatment
 - Persistent neuropsychiatric symptoms, defined as a score of 4 or higher on any one item or a total score of 40 or higher on the BPRS assessment at the 48-hour, post-dose evaluation
 - Paresthesia that interferes with any activity
 - Athetoid movement
- Cardiac
 - Hypertension, which cannot be explained by agitation or other behavioral symptoms, requiring antihypertensive medication
 - Cardiac arrhythmias or changes that are deemed clinically significant but do not cause the subject to be hemodynamically unstable
 - QTc is > 450 msec for males or >470 msec for females and has increased > 60 msec from baseline;
 - Supraventricular tachycardia alone without hemodynamic compromise
 - Bigeminy or trigeminy not associated with hypotension
- Renal
 - Increase of serum creatinine by ≥ 0.3 mg/dL (≥ 26.4 $\mu\text{mol/L}$) or increase to $\geq 150\%$ from baseline or urine output < 0.5 mL/kg/hour for > 6 hours
- Injection Site Reaction
 - Any reaction determined to be severe, as defined by the FDA's guidance¹ for injection site reactions (See protocol Appendix B).

5.1.3 Adverse Events (AEs)

The term “AE,” as used by the Sponsor, is synonymous with the term “adverse experience,” which is used by the FDA. Any condition recorded on the medical history should not be reported as an AE unless it worsens in frequency, intensity, or severity, or there are clinically significant changes in laboratory values after administration of study drug. An AE or suspected adverse reaction is considered “unexpected” if it is not listed in the investigator's brochure or is not listed at the specificity or severity that has been observed or, if an investigator's brochure is not required or available, is not consistent with the risk information described in the general investigational plan or elsewhere in the current application, as amended. “Unexpected,” as used

¹ <https://www.fda.gov/regulatory-information/search-fda-guidance-documents/toxicity-grading-scale-healthy-adult-and-adolescent-volunteers-enrolled-preventive-vaccine-clinical>

in this definition, also refers to AEs or suspected adverse reactions that are mentioned in the investigator's brochure as occurring with a class of drugs or as anticipated from the pharmacological properties of the drug but are not specifically mentioned as occurring with the particular drug under investigation.

Note: A procedure is not an AE, but the reason for a procedure may be an AE.

The time frame for the collection of AEs and SAEs begins at the administration of investigational product through 30 days after the investigational product is administered.

5.1.3.1 Severity

All AEs will be assessed for severity by an investigator. Inherent in this assessment is the medical and clinical consideration of all information surrounding the event including any medical intervention required. The *Common Terminology Criteria for Adverse Events (CTCAE)*, version 5.0 (November 27, 2017) is a descriptive terminology that will be utilized for grading all AEs, with the exception of injection site reactions, which will be graded using the *Local Reaction to Injectable Product* table from the FDA's *Guidance for Industry: Toxicity Grading Scale for Healthy Adult and Adolescent Volunteers Enrolled in Preventive Vaccine Clinical Trials* (*see protocol* Appendix B).

Both guidance documents provide a grading (severity) scale for each AE term. Each event will be assigned one of the following categories: mild (grade 1), moderate (grade 2), severe (grade 3), or potentially life threatening (grade 4).

Note that use of rescue medications may be appropriate in response to the SAEs.

